Visits	V1a ²	V1b ²	V2 ¹⁵	V3 ¹⁵	V4	V5	V6	V7	V8	EoT ¹²	EDV ³	UNS ¹
Days / Weeks after V1b			+7 days	+37 days	+12 weeks	+26 weeks	+38 weeks	+52 weeks	+64 weeks	+78 weeks		
On-site visit ⊗/telephone contact ☎	⊗	⊗	⊗	⊗	☎	⊗	☎	⊗	☎	⊗	⊗	⊗/☎
Day	-3 to -1	1 (within 96 h after stroke)	8±2	38+4	85±10	183±10	267±10	365±10	449±10	547±10		
Safety												
Adverse events (AEs)	●	●	●	●	●	●	●	●	●	●	●	●
Vital signs (blood pressure, heart rate, tympanic body temperature)	●		●	●		●		●		●	● (●)	
Blood withdrawal (haematology and biochemistry) ⁶	●		●	●							● ¹³	(●)
Urinalysis	●		●	●							● ¹³	(●)
12-lead electrocardiogram (ECG)	● ⁴		●	●							● ¹³	(●)
Physical and neurological examination	●		●	●		●		●		●	●	(●)
Serum pregnancy test ⁷	●											
Urine pregnancy test ⁷	●		●	●							● ¹³	(●)

1. Unscheduled visits (UNSSs) will be performed at the discretion of the investigator. Assessments in brackets are optional and can be performed at the discretion of the investigator.
2. If all conditions for V1a and V1b are fulfilled, V1a and V1b can be performed on the same day.
3. An early discontinuation visit (EDV) should be performed within 10 days, if possible, on withdrawal.
4. If examination was done after primary stroke, the results should be used and the examination does not need to be repeated at V1a.
5. EEGs are optional assessments and will be performed at the discretion of the investigator.
6. Including eGFR and coagulation. At V1a also thyroid function.
7. Only in women of childbearing potential. Frequency may be adapted to meet specific country-specific/local requirements.
8. The diary will only be reviewed but not be collected at V1b.
9. If a patient is unable to give written or verbal consent at V1a, patient consent can be deferred or the patient's legal representative must provide written informed consent (according to country specific requirements). Written or verbal witnessed informed consent from the patient must be obtained until V2.
10. Only applicable for patients who were unable to give informed consent at V1a.
11. The scores for "Severity of stroke, Large-artery atherosclerotic aetiology, Early seizures, Cortical involvement, Territory of middle cerebral artery" (SeLECT score) in patients with an acute ischaemic stroke and for "Cortical involvement, Age < 65 years, Volume of intracerebral haemorrhage > 10 mL and Early seizure within 7 days after intracerebral haemorrhage" (CAVE score) in patients with acute intracerebral haemorrhage.

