**Table 3: Visit Slotting**

Visit Slot/ Label	Target Day	Description
V1a	-	Screening/baseline, within 120 hours after stroke, or since last time seen well
V1b	1	Day 1, within 120 hours after stroke, or since last time seen well
V2	8	Closest non missing assessment to target day between study day 2 and 31
V3	38	Closest non missing assessment to target day between study day 32 and 71
V4	85	Closest non missing assessment to target day between study day 72 and 171
V5	183	Closest non missing assessment to target day between study day 172 and 242
V6	267	Closest non missing assessment to target day between study day 243 and 353
V7	365	Closest non missing assessment to target day between study day 354 and 437
V8	449	Closest non missing assessment to target day between study day 438 and 533
EOT	547	Closest non missing assessment to target day between study day 534 and >547

EDV	EDV	Early discontinuation visit
-----	-----	-----------------------------

If, for any variable, a visit was not scheduled (e.g. V4 for vital signs), the respective measurement will be assigned to the visit slot with the closest target day where a visit was scheduled. If two measurements fall into that slot, the closest one to target day will be used.

If, for any safety variable, V1b is not scheduled and a measurement is taken on Study Day 1, this measurement will be slotted to V2 if the assessment was done after first IMP intake.

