## **Endpoint value**

The endpoint value for an efficacy variable is defined as the last non-missing value collected after first intake of IMP before or at the respective endpoint (within the time window of interest i.e. 6 month-period, 12 month-period and 18 month-period).

The endpoint for a safety variable is defined as the last non-missing value collected after first intake of IMP that is no baseline value.

**Absolute change from baseline** will be calculated as

$$\text{Absolute Change from Baseline at Visit } X = \text{Value at Visit } X - \text{Baseline Value}$$

**Relative change from baseline (%)** will be calculated as

$$\text{Relative Change from Baseline at Visit } X = \frac{\text{Value at Visit } X - \text{Baseline Value}}{\text{Baseline Value}} \times 100$$

Note: Patients with a baseline value of '0' will be excluded from the calculation of relative change.

See section 5.4.1 for the definition of first and last IMP intakes.

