## **5.6.2 Clinical Laboratory Evaluation**

Clinical laboratory values (haematology, biochemistry, including eGFR and coagulation, urinalysis) are collected at V1a, V2, V3, EDV (if EDV performed before V3) and, if applicable, UNS for each laboratory parameter. Thyroid function will be assessed at V1a.

A serum pregnancy test at V1a and urine pregnancy tests at V1a, V2, V3, EDV (if EDV performed before V3) and, if applicable, UNS will be performed for all females of childbearing potential.

The following parameters are collected:

**Haematology:** Haemoglobin, haematocrit, red blood cell (RBC) count, white blood cell (WBC) count, differential - neutrophils, eosinophils, lymphocytes, monocytes and basophils, and platelet count.

**Biochemistry:** Sodium, potassium, chloride, calcium, phosphate, blood urea nitrogen, aspartate transaminase (AST), alanine transaminase (ALT), gamma-glutamyl transferase (GGT), lactate dehydrogenase (LDH), alkaline phosphatase, creatine phosphokinase (CPK), creatinine, glucose, C-reactive protein, albumin, total protein, total cholesterol, low-density lipoprotein-cholesterol, high-density lipoprotein-cholesterol, triglycerides, and total bilirubin (bilirubin will be fractionated direct/indirect if elevated).

Sodium levels will be monitored for signs of **hyponatraemia**. Patients will be classified by their minimum post-baseline sodium level according to the following categories:

$\geq 135$  mEq/L

130 -  $< 135$  mEq/L

125 -  $< 130$  mEq/L

$< 125$  mEq/L

and for any decrease from baseline  $> 10$  mEq/L.

**eGFR** will be estimated based on serum creatinine value (see CTP 11.4.3).

**Coagulation:** INR and activated partial thromboplastin time (aPTT).

**Thyroid function (at V1a only):** total triiodothyronine, free triiodothyronine, total thyroxine, free thyroxine, thyroid stimulating hormone.

**Serum pregnancy test (at V1a only):**  $\beta$ -hCG in females of childbearing potential.

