[Table 15.3.2.4.1 Clinical Laboratory Tests: Shift Table of Haematology Results from Baseline to Worst Post Baseline Value – Safety Set](#)

[Table 15.3.2.4.2 Clinical Laboratory Tests: Shift Table of Biochemistry Results from Baseline to Worst Post Baseline Value – Safety Set](#)

[Table 15.3.2.4.3 Clinical Laboratory Tests: Shift Table of Coagulation Results from Baseline to Worst Post Baseline Value – Safety Set](#)

Shift tables showing changes in the number and frequency of patients with respect to the normal range and clinical significance between baseline and the worst-post-baseline-value by treatment will be provided. Patients with missing data will be presented as part of a “missing” category.

[Table 15.3.2.5.1 Clinical Laboratory Tests: Incidence Clinically Significant Urinalysis Results \(Local Dipstick\) – Safety Set](#)

Clinically significant values of urinalysis parameters (collected using local dipstick) will be summarised by visit using default frequency tabulation by treatment group and in total. The number of patients with any CS abnormalities will be summarised. Visit Slots will be used.

[Table 15.3.2.5.2 Clinical Laboratory Tests: Incidence of Urinalysis Results \(Central Laboratory\) – Safety Set](#)

Clinically significant values of urinalysis parameters (provided by central laboratory) will be summarised by visit using default frequency tabulation by treatment group and in total. The number of patients with any CS abnormalities will be summarised. Visit Slots will be used.

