### **5.6.4 12-Lead Electrocardiogram Data**

A standard 12-lead electrocardiogram (ECG) is performed at V1a, V2, V3, EDV (if EDV performed before V3) and, if applicable, UNS.

If an ECG was done after primary stroke, the results will be used and the examination does not need to be repeated at V1a. ECG assessment after primary stroke, if available, otherwise the last collected value before IMP intake will be defined as baseline value.

ECG results will be assessed by an investigator if normal, abnormal or CS abnormal and assessments will be documented in the eCRF.

The following statistical outputs will be presented:

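### Laboratory Endpoint, worst post-baseline value and minimum sodium have no last day, so a discretionary test long after dosing can replace or override the V3 result

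*SAP*

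**What the plan says.** SAP 4.8 gives two Endpoint definitions. For efficacy variables the last value must lie "within the time window of interest i.e. 6 month-period, 12 month-period and 18 month-period". For safety variables the rule is "The endpoint for a safety variable is defined as the last non-missing value collected after first intake of IMP that is no baseline value", with no closing day.

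SAP 5.6.2 says that laboratory values "are collected at V1a, V2, V3, EDV (if EDV performed before V3) and, if applicable, UNS for each laboratory parameter". SAP 5.6.4 says that the ECG "is performed at V1a, V2, V3, EDV (if EDV performed before V3) and, if applicable, UNS". Footnote 1 to the protocol's schedule of procedures says that unscheduled visits "will be performed at the discretion of the investigator. Assessments in brackets are optional". No last day is given for them.

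The laboratory outputs in 5.6.2 include summaries and baseline-to-Endpoint shift tables. They also include shift tables "between baseline and the worst-post-baseline-value by treatment will be provided", and a classification of each patient by the lowest sodium after baseline. None of these carries a time window.

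For V3, Table 3 in SAP 4.5 reads "Closest non missing assessment to target day between study day 32 and 71". Below the table, for a variable with no visit scheduled at that point, "the respective measurement will be assigned to the visit slot with the closest target day where a visit was scheduled". If two values then share a slot, the one nearer the target day is used.

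**The concern.** The drug is taken for about five weeks and laboratory safety is scheduled only around that period, yet follow-up lasts 18 months. A rule that takes the last or worst value without a closing day lets a result obtained long after the drug was stopped stand as the patient's laboratory outcome. After a first unprovoked seizure the patient is treated at the investigator's discretion (SAP 2.3), so a late value may also reflect other treatment.

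What is at stake is the reading of the laboratory shift tables, and of sodium in particular, which 5.6.2 singles out for monitoring. SAP 5.6.1 limits treatment-emergent adverse events by default to 14 days after the last intake. The same low sodium a year later would fall outside that default if reported as an adverse event, but would enter the biochemistry shift tables as a laboratory value. No efficacy result is touched.

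**Working it through.** **Inputs**
- Last planned dose: Day 30 (half-tablet patients) or Day 37 (one-tablet patients after down-titration), SAP 2.5.
- Last scheduled laboratory test: V3, target Day 38; an early discontinuation visit has laboratory tests only if it precedes V3, SAP 5.6.2.
- End of follow-up: 78 weeks after V1b, Day 547, with a window of 10 days either side, SAP Table 2 and 4.7.
- V3 slot: Days 32 to 71. Target days of the post-baseline laboratory and ECG slots: 8 (V2) and 38 (V3), SAP Table 3.

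**Step 1: the plan's own end day.** 78 × 7 + 1 = Day 547, which matches SAP 4.7.

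**Step 2: longest gap between last planned dose and a late test** (1 month = 365.25/12 = 30.44 days)
- Last dose Day 30: 547 − 30 = 517 days; 517/30.44 = 17.0 months.
- Last dose Day 37: 547 − 37 = 510 days; 510/30.44 = 16.8 months.
- At the upper edge of the final visit window, Day 557: 527 and 520 days, or 17.3 and 17.1 months. A patient who stops the drug early has a longer gap.

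**Step 3: which slot a late value goes to.** Distance to V2 is d − 8 and to V3 is d − 38, so V3 is always the nearer for a late day d.
- Day 72, the first day after the V3 slot: 64 days from V2, 34 from V3.
- Day 547: 539 days from V2, 509 from V3.

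Every laboratory or ECG value after Day 71 is thus directed to V3 by the text below Table 3, whereas the table closes V3 at Day 71. The late value is used only if the patient has nothing nearer to Day 38.

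**Step 4: the rules applied to one hypothetical patient.** Dosing to Day 37, V3 sample on Day 38, one unscheduled sample on Day 400 (400 − 37 = 363 days after the last dose).
- V3 slot: Day 38 is kept, being closest to target.
- Endpoint: Day 400 replaces Day 38, because it is the last value.
- Worst value and minimum sodium: the more extreme of all values, including Day 400.
- If the V3 sample is missing and nothing else lies nearer, Day 400 is also shown as V3.

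**Step 5: which variables are exposed.** Laboratory variables are exposed through Endpoint, worst value and minimum sodium, and through an empty V3 slot. The single ECG table in 5.6.4 is by visit slot, with no Endpoint, worst-value or shift output, so ECG is exposed only through an empty V3 slot.

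**The case against.** The strongest reply is that the open Endpoint rule is general and suits most of what it serves: vital signs and PHQ-9 question 9 are scheduled to the end of trial. That stands. What is missing is an exception for laboratory variables, not a new rule for all of safety.

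It can also be said that on-treatment results stay visible elsewhere. Sodium categories are tabulated by visit slot, and the closest-to-target rule protects V3 whenever a proper V3 value exists. A late value cannot erase an on-treatment abnormality from a minimum or worst value. This is right, and it narrows the harm: Endpoint can lose the on-treatment result, while the worst value and the minimum can only gain an off-drug abnormality. Nor is the text below Table 3 without purpose. SAP 4.5 expects pandemic delays and names no maximum, so that text rescues a V3 sample drawn on, say, Day 75.

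A reader might go further and infer that late tests are done for cause, cluster in the arm with more seizures, and so make ESL look safer. The documents do not support this. Unscheduled tests are discretionary and optional, and nothing ties them to seizures. The planning rates of 26% and 8% are failure rates that include deaths (in SAP 2.6 also other missing data), and they count seizures before Day 71. If a share q of failures led to a late test, the counts per 100 would be 26q against 8q: 0 against 0 at q = 0, and 26 against 8 at q = 1. The documents give no q. Nor does the fact that Days 72 to 547 make up 476/547 = 87% of follow-up say what share of laboratory values is late.

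**Conclusion.** The point holds for laboratory variables. As written, any unscheduled test after V3 becomes the laboratory Endpoint, and it counts towards the worst value and the minimum sodium, up to 16.8 to 17.0 months after the last planned dose. The slotting text and Table 3 disagree on whether a laboratory or ECG value after Day 71 can be V3, and must be reconciled.

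The size in patients is unknown. The effect is nil if no late tests were done, and the documents do not give their number or their split by arm. No bias towards either arm is asserted. The day counts assume planned dosing and follow-up to Day 547. This is a modest defect in safety reporting that is worth correcting because the correction is cheap.

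**What to change.** - **SAP 4.8 and 5.6.2:** restrict laboratory Endpoint, worst post-baseline value and minimum post-baseline sodium to assessments from first intake to Day 71, plus the patient's scheduled V3 sample if it was delayed beyond that day.
- **SAP 4.5:** state that unscheduled laboratory and ECG values after Day 71 are not slotted to V3.
- **Outputs:** show later unscheduled values in a separate follow-up row or in the listings.
- **Leave unchanged:** the Endpoint rule for vital signs and PHQ-9 question 9.

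Day 71 is the SAP's own V3 limit, but it is not a strict on-treatment limit: it lies 71 − 37 = 34 to 71 − 30 = 41 days after the last planned dose. Using the adverse-event window instead would end at Day 44 or 51 for completers. It could, however, exclude V3 itself for early stoppers (last dose Day 8 gives 8 + 14 = Day 22), who would then need their own row.

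The cost is wording in three sections and one date filter with a flag for delayed V3 samples. The downside is that late abnormal laboratory values no longer appear in the shift tables.

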## **4.9 Coding Systems and Conventions**

### **4.9.1 Coding of adverse events and medical history**

Adverse event and medical history investigator terms are assigned to a lowest level term (LLT) and a preferred term (PT) and will be classified by high level term (HLT), high level group term (HLGT) and system organ class (SOC) according to the Medical Dictionary for Regulatory Activities (MedDRA), in the version as specified in the Data Management Plan (DMP) [2].

### **4.9.2 Coding of medications**

Medications are classified according to active drug substance using the World Health Organization-(WHO) drug dictionary WHODrug Global, version as specified in the DMP [3]. The WHO drug code has 11 digits. The generic name is defined by the first 6 of the 11 digits. In addition, the Anatomical Therapeutic Chemical (ATC) classes are assigned to the drug code. In this study, ATC codes are defined to the 4th level.

### **4.9.3 Coding of therapies**

Therapies investigator terms are assigned to preferred term (PT) and System Organ Class (SOC) using the Medical Dictionary for Regulatory Activities (MedDRA), in the version as specified in the Data Management Plan (DMP) [2].

## **4.10 Handling of Missing Data**

The analysis of missing data impact on the primary efficacy endpoint is described in the Section 5.5.1.1.

All other data will be analysed as reported and missing data will not be imputed.

## 5. STATISTICAL ANALYSIS: DEFINITIONS, DERIVATIONS, CALCULATIONS AND METHODOLOGY

### 5.1 Patient Disposition

#### 5.1.1 Disposition and Withdrawals

The following disposition data will be collected:

- Did the patient give his/her informed consent?
  - if Yes, date of written informed consent or date of verbal witnessed informed consent
  - if No, reasons for IC absence:
    - a) the patient refused to give his/her consent or
    - b) the patient died or
    - c) the patient did not regain the ability to give consent.
  - d) Only applicable for Portugal: a legal representative gave his/her informed consent at V1a
- deferred consent date or date of legal representative's consent (if patient was unable to give written or verbal consent at V1a)
- date and time of first IMP intake
- time (h) of first IMP intake after primary stroke
- date of last IMP intake
- date of trial termination
- did the patient complete the 6/ 12/ 18 month period (yes,no)
- did the patient complete the trial as scheduled (yes, no)
- primary reason for premature trial termination, including specification

**Screening failures** will be all patients who have been enrolled in the trial (i.e. ICF signed by patient, by witness in case of verbal consent or by patient's legal representative or deferral of informed consent adequately documented and signed by the investigator), but discontinue the trial prior to randomisation at V1b due to whatever reason (withdrawal of consent by patient or legal representative, do not fulfil criteria, by decision of investigator, etc.).

**Withdrawals** will be all patients who have been enrolled and, for whatever reason, discontinue the trial after randomisation at V1b. Patients may be withdrawn from the trial at any time, either on their own or upon legal representative request or at the discretion of the investigator.

The following statistical outputs will be provided:

#### Table 15.1.1.1 Analysis Sets – Enrolled Set

The number and percentage of patients included in the enrolled, randomised, safety, full analysis, per-protocol and EEG analysis sets will be provided by treatment group and in total. Percentages will be based on the number of patients in the enrolled set. Date of first patient first visit and date of last patient last visit will be displayed.

#### Table 15.1.1.2 Reasons for Exclusions from Analysis Sets – Randomised Set

The number and percentage of patients excluded from the safety, full analysis and per-protocol sets will be provided by treatment group and in total. Percentages will be based on the number of patients in the randomised set. The reasons of exclusion from the analysis sets will be incorporated into the table.

#### Table 15.1.2 Screening Failures – Enrolled Set

Counts and percentages of patients who discontinued the study during the screening phase prior to randomisation to treatment will be summarised by reasons associated with the discontinuation. Percentages will be based on the number of patients in the enrolled set.

#### Table 15.1.3 Patient Disposition – Safety Set

Counts and percentages of patients who completed the 6-month-period, the 12-month-period, the 18-month-period (= patients who completed the trial as scheduled) and patients who prematurely

terminated the trial will be summarised by treatment group and in total. Reasons for discontinuation will be included. Percentages will be based on the number of patients in the safety set.

**Table 15.1.4.1.1 Number of Patients by Country and Site – Enrolled Set**

Counts and percentages of patients in each country and site in total. Percentages will be based on the number of patients in the enrolled set.

**Table 15.1.4.1.2 Number of Patients by Country and Site – Safety Set**

Counts and percentages of patients in each country and site by treatment group and in total. Percentages will be based on the number of patients in the safety set.

**Table 15.1.4.2.1 Number of Patients by Visit – Safety Set**

Counts and percentages of patients attending each scheduled visit will be presented by treatment and in total. Percentages will be based on the number of patients in the respective set.

**Figure 15.1.1 Flow Chart of Patient Disposition – Enrolled Set**

The number of patients with the occurrence of each protocol milestone (Enrolment, Randomisation, Completion) will be displayed. The number of screening failures and discontinuations as well as their reasons will also be summarised.

**Figure 15.1.2 Flow Chart of Analysis Sets – Enrolled Set**

The number of patients in each analysis set will be displayed.

**Listing 16.2.1.1 Patient Disposition – Randomised Set**

The disposition data including the informed consent date and type, first and last IMP intake date, trial termination date, if the patient completed the trial as scheduled (yes/no) and reasons for premature termination (if applicable) will be listed by treatment group.

**Listing 16.2.1.2 Screening Failures – Enrolled Set**

Patients who discontinued the study prior to the randomisation to treatment will be listed. Informed consent data and type, reason in case of informed consent absence and reasons for premature trial termination will be displayed.

